9.5.2 Sample size of external comparison groups (LEMTRADA non-exposed)

Sample size is set at 125 in comparison Cohorts II and III respectively in "AUBAGIO (teriflunomide) Pregnancy Outcome Exposure Registry: an OTIS Autoimmune Disease in Pregnancy Project" (Genzyme study OBS13499)." For the sample size calculation above, it is assumed that a sample size of 125 in the comparator group includes 4% missing data and 2% were exposed to LEMTRADA (in Cohort II), resulting in 125*96%*98% = 117 subjects.

9.6 DATA MANAGEMENT

9.6.1 Data collection schedule

Table 2 - study data collection schedule

Data collected/ Evaluation	Enrolment Interview (ideally <13 weeks' gestation)	2nd Trimester Interview (16-20 weeks' gestation)	3rd Trimester Interview (26-32 weeks' gestation)	Pregnancy Outcome Interview (within 6 weeks after the end of the pregnancy) ab	Infant Status Update (1 year after delivery) b	Targeted Follow- up (after BDE review ^C	Retrospective Pregnancy (pregnancy outcome known at time of enrollment)
Enrollment and Informed Consent	Х						Χ
Contact Information and Demographics	X						Х
Targeted Medical History	X					X	Χ
Pregnancy History	X						Χ
Risk Factors d	X	X	X			Χ	Χ
LEMTRADA Exposure History ⁶	X						X
Concomitant Medications ^f	X	Х	Х	Х			X
Pregnancy Status/Outcome		Х	Х	X		Х	Х
Foetal/Pediatric Outcomes				Х	X	Х	Х
Medical Record Review of Pregnancy Outcome				Х		Х	Х
HCP Questionnaire on Infant Status at 1 Year					Χg		Х
Collection of selected adverse events ^h	Х	Х	Х	Х	Х	Х	Х

- a The interview can be conducted by phone or in person. Whenever medical documentation is needed (summary from maternity, other hospitalization or investigation summaries, etc.), they can be collected by electronic transfer
- b Active contact by national Coordinator, if needed, not later, than 6 weeks after expected delivery date and 1 year after delivery for live birth
- c Obtain this information if information is requested following Birth Defect Evaluator review
- d Risk factors: Smoking, alcohol use, illicit drug use, pre-pregnancy body mass index (BMI), etc....
- e Exposure history for current pregnancy only
- f All medications for MS from the onset, also other medications relevant to the disease or ongoing within 1 month to inclusion
- g For live-birth outcomes only, if woman has not withdrawn consent
- h AEs to be reported include: a) all serious adverse events, including medically important events and pregnancy outcome related events such as all major and minor malformations, spontaneous abortions, stillbirths, elective terminations, neonatal deaths ,preterm birth, small for gestational age at birth, and any other adverse pregnancy outcomes occurring in a LEMTRADA-exposed pregnancy; b) non serious AEs, which to the opinion of HCP or National Coordinator may potentially have impact on the outcome of the pregnancy, whether causally related to the drug product or not.

NOTE: BDE=Birth Defect Evaluator

Property of the Sanofi Group - strictly confidential

9.6.2 Data collected

9.6.2.1 Date collected from the mother (patient) by Health Care Provider (HCP)

Once patients sign the informed consent, patients' enrollment and follow up information are collected by the HCP. Whenever permitted in local legislation, signature of ICF will mean that the pregnant patient consents that medical records of herself and of the infant can be released by the HCP to the NC for further use in this Registry. After the ICF is signed, the enrolment interview can be done by HCP or registry staff if the HCP is not available; follow-up interviews can be done by phone or in person (by HCP or registry staff). Forms with patients' data completed by the HCP are sent to the National Coordinator by mail, fax, or email (on a secure server). Upon receipt, the National Coordinator reviews the forms for completeness, queries the HCP for missing data, and de-identifies and key-codes all forms before entering them into the CRF. Information to be collected during maternal interviews includes:

- Demographics: maternal age, maternal race/ethnicity (as per local regulations), education, family income category.
 - Of note: Patient race or ethnicity (e.g., "Caucasian/White, Black, Asian/Oriental, Others" will be collected in this study because these data are required by several regulatory authorities (e.g., on afro American population for Food and Drug Administration (FDA), on Japanese population for the PMDA in Japan, or on Chinese population for the CFDA in China)"
- Targeted medical history including prior treatment for MS.
- History of previous pregnancies and outcomes of each:
 - Pregnancy outcome: live birth, stillbirth, spontaneous abortion, induced abortion,
 - Pregnancy complications,
 - Fetal/neonatal abnormalities and type.
- Current pregnancy: fertility treatments (if applicable), date of last menstrual period, expected delivery date, prenatal tests conducted and results, pregnancy status.
- Risk factors: Smoking, alcohol use, illicit drug use, pre-pregnancy BMI
- LEMTRADA exposure (infusion dates).
- Concomitant medications including over-the-counter and prescription medications, vitamin supplements including folic acid, herbal medicines from one month prior to the date of enrollment.
- At pregnancy completion (as applicable depending on pregnancy outcome)
 - Pregnancy outcome (live birth, spontaneous abortion, stillbirth, induced abortion) and type (singleton or multiple),
 - For live births.

- a) Gender, gestational age at delivery, mode of delivery, type/length of hospital stay, maternal and neonatal complications, maternal weight gain, presence or absence of major and minor structural defects, Apgar scores, birth weight, birth length, and head circumference.
- For other outcomes.
- a) Gestational age at time of event, pathology results if available, and presence or absence of major and minor structural defects. For stillborn infants gender, birth size, and autopsy results.
- Safety data
 - All SAEs including medically important events (see Section 11.1.1 for details),
 - All non-serious adverse events which per opinion of HCP/National Coordinator potentially have an impact on pregnancy outcomes.

At the conclusion of the pregnancy outcome interview, upon local practice, when local legislation requires this in addition to ICF signature, women can be mailed a packet with medical records release forms (or equivalent) from the pre- and postnatal HCP, the delivery hospital, and the pediatrician. Women will be asked to sign the medical records release forms and return the signed forms to the HCP(s). This process is to allow the National Coordinator to contact HCPs to confirm pregnancy outcomes and other above described data.

For retrospective cases, all data collections described above are applicable except that there would be no trimester interviews because the pregnancy outcome is already known.

Targeted follow-up

If a birth defect is noted, additional details regarding the birth defect may be requested from HCP by NC or by BDE to further define the etiology, facilitate classification, and to assess the presence of potential confounders of the birth defects. In addition, any specific questions the BDE (see Section 9.4) might have following initial review of the case will be included on the Targeted Follow-up Form.

The Targeted Follow-up Form collects the following from the reporter of the birth defect(s) or other appropriate HCP:

- Additional details of the birth defect (from initial report)
 - Assessment of etiology from HCP perspective
 - Requirement of surgical intervention to treat the birth defect (if so, dates and details)
- Potentially contributory factors
 - Medications or other products or agents taken during pregnancy
 - Maternal and paternal occupation
 - Concurrent medical/clinical conditions (occurring prior to and/or during pregnancy)
 - Any other factors that might have contributed to this outcome

- Specific targeted questions requested by the Birth Defect Evaluator reviewing the case relevant to this birth defect/outcome of interest
- Additional comments addressing factors that may have had an impact on the pregnancy outcome, birth defect, or other outcome of interest.

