9 RESEARCH METHODS

9.1 STUDY DESIGN

This post authorization safety study (PASS) is an international, observational cohort (registry) of pregnancy outcomes in women with MS exposed to LEMTRADA during pregnancy.

Pregnancy outcomes in women exposed to LEMTRADA will be compared with available data from external comparison groups: women with MS not exposed to LEMTRADA, and women without MS (details defined in Section 4, under "Data source").

This is an observational study with no experimental intervention utilized. Women enrolled in the study may receive treatment and evaluations for their MS and their pregnancies as determined by their treating physicians in accordance with local standard of care. Information of prospective pregnancies on patient's safety and pregnancy outcome will be collected during each trimester and within 6 weeks after the end of pregnancy. For all live births, the infant's HCP will be contacted at 1 year post delivery to obtain follow-up on the infant's health status. Information of retrospective pregnancies (exposed to LEMTRADA during pregnancy but pregnancy outcome is known at time of registry) will be collected similarly except for information on the chronological interview during pregnancy.

Women who were pregnant or became pregnant within the period of time between their initiating a course of treatment with LEMTRADA to 4 months after their last infusion for that course may be enrolled, provided their pregnancy is ongoing.

A total of approximately 204 women exposed to LEMTRADA during pregnancy (prospective) will be enrolled to achieve approximately 193 women followed up to 1 year post-delivery. Retrospective pregnancies are not part of this sample size calculation and are collected additionally.

Women exposed to LEMTRADA during pregnancy will be recruited from a variety of sources, including referral of female patients who become pregnant while enrolled in a separate observational study; referral of LEMTRADA-exposed female patients reporting pregnancies identified through routine pharmacovigilance activities, and LEMTRADA-exposed female patients reporting pregnancies identified through study outreach activities such as study postings on applicable websites. Enrollment as early in the pregnancy as possible is encouraged. Study enrollment is voluntary and requires informed consent in accordance with local requirements.

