9.7.4.3 Criteria obtained from comparison cohorts

The following comparison groups in the AUBAGIO® (teriflunomide) North American pregnancy exposure registry (Genzyme study OBS13499) will be used:

- Cohort II (North American AUBAGIO Pregnancy Outcome Exposure Registry Cohort II) -pregnant women with MS not exposed to AUBAGIO during the current pregnancy modified to also exclude women exposed to LEMTRADA
- Cohort III (North American AUBAGIO Pregnancy Outcome Exposure Registry Cohort III) pregnant women without MS and not exposed to AUBAGIO during the current pregnancy modified to also exclude women exposed to LEMTRADA

NOTE: Cohort I (pregnant women with MS exposed to AUBAGIO) are excluded

Patient-level data from the AUBAGIO pregnancy registry are made available to the sponsor (Genzyme, a Sanofi Company) when data has been stripped of personal identifiers.

Following variables will be collected:

- Maternal age
- Maternal race/ethnicity
- Socioeconomic status
- Prior pregnancy history: gravidity/parity and previous outcomes
- Periconceptional use of folic acid containing supplements
- Unintended pregnancy
- Gestational age at enrollment
- Exposure to other medications (including known teratogens) and other MS medications
- Comorbidities
- Disease severity measure(s)

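### For non-MS medicines, folic acid and herbal products the look-back is tied to enrolment, not to LMP or conception, so early-pregnancy use is incompletely recorded and not comparable with the comparison cohorts

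*Protocol*

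**What the plan says.** Section 9.6.2.1 lists what the maternal interviews collect. The item on co-medication reads "Concomitant medications including over-the-counter and prescription medications, vitamin supplements including folic acid, herbal medicines from one month prior to the date of enrollment". Footnote f to Table 2 (section 9.6.1) puts it differently: "All medications for MS from the onset, also other medications relevant to the disease or ongoing within 1 month to inclusion". Both limits run back from enrolment or inclusion. The list in 9.6.2.1 also includes "Targeted medical history including prior treatment for MS", the LEMTRADA infusion dates and the LMP date.

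Table 2 labels the first contact "Enrolment Interview (ideally <13 weeks' gestation", and section 9.1 adds "Enrollment as early in the pregnancy as possible is encouraged". For prospective women the only stated limit is that the pregnancy is still ongoing. Table 2 schedules concomitant medications again at the second-trimester, third-trimester and outcome interviews and for retrospective pregnancies, always under footnote f.

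For the comparison cohorts, section 9.7.4.3 lists "Periconceptional use of folic acid containing supplements" as well as exposure to other medications, known teratogens included. Section 9.7.5 allows propensity-score matching and covariate adjustment where the data permit, and gives other medications as one example of a confounder.

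When a birth defect has been noted, the Targeted Follow-up Form (section 9.6.2.1) can ask for "Medications or other products or agents taken during pregnancy".

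**The concern.** The relevant time for teratogen exposure and periconceptional folic acid is fixed by conception. The look-back is fixed by the date on which a woman happens to enrol. A medicine or supplement stopped more than a month before enrolment is not asked for, and later interviews under the same footnote do not clearly reopen those weeks.

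The comparison cohorts are to deliver a periconceptional variable and the exposed group an enrolment-based one, so the same covariate would describe different periods in the two groups. The error can go both ways. Folic acid begun once the pregnancy was known and still taken at enrolment is recorded as use, although it says nothing about conception. A drug taken in week 5 and stopped may not be recorded at all. How much is lost depends on gestational age at enrolment, which section 9.7.5 itself lists as a possible confounder. An SAP cannot recover data that were never collected.

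**Working it through.** The protocol gives no figure on this point to reproduce, so the check is date arithmetic.

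**Inputs from the protocol:** look-back of one month before enrolment (9.6.2.1; Table 2, footnote f); enrolment ideally before 13 weeks, with no upper limit while the pregnancy is ongoing (Table 2; 9.1).

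**Assumptions, not in the protocol:** weeks counted from LMP; conception at week 2; organogenesis about weeks 5 to 10; one month = 30.4 days, that is 30.4 / 7 = 4.34 weeks.

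**Formulas:** window start s = g − 4.34, where g is the week at enrolment. From s onward, use is covered by the look-back and the later interviews. Share of weeks 5–10 covered = (10 − max(5, s)) / 5, limited to the range 0 to 1.

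| Enrolment week g | Window opens, s | Conception (week 2) covered | Share of weeks 5–10 covered |
|---|---|---|---|
| 6 | 1.66 | yes | 100% |
| 8 | 3.66 | no | 100% |
| 10 | 5.66 | no | 4.34 / 5 = 87% |
| 12 | 7.66 | no | 2.34 / 5 = 47% |
| 13 | 8.66 | no | 1.34 / 5 = 27% |
| 16 | 11.66 | no | 0% |
| 20 | 15.66 | no | 0% |

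**Limits:**
- Conception is inside the window if g ≤ 2 + 4.34 = 6.34.
- Weeks 5–10 are fully inside if g ≤ 5 + 4.34 = 9.34.
- A full month before conception is inside only if g ≤ 2, which is not practicable.

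**Sensitivity to the week count.** Appendix A dates some outcomes from the estimated date of conception. If Table 2 counted weeks that way, enrolment at week 12 would be LMP week 14. The window would open at 14 − 4.34 = 9.66, and the share covered would fall to (10 − 9.66) / 5 = 7%. Counting from LMP is thus the milder reading.

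**Retrospective pregnancies.** Section 9.6.2.1 applies the same items to them. If enrolment comes more than one month after the pregnancy ended, the window opens after that end and contains none of the pregnancy.

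**What the window does catch.** Any product still in use after s is recorded whenever it began, but the protocol text does not say that start and stop dates are taken. MS medications are outside this limit. On its most natural reading, footnote f also takes other medicines relevant to the disease without the one-month limit.

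**The case against.** Several things limit the point, and they stand. MS drugs, arguably the most important co-exposure here, are recorded from onset. Enrolment by about week 9 covers weeks 5–10 in full, and early enrolment is encouraged. Continuing use is captured. The stated comparison in 9.7.5 is a relative risk with its 95% CI against each group; adjustment is optional, depends on the data being available, and folic acid is not among the factors named. Retrospective pregnancies are only described.

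A reader might infer more than this supports:

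- **That the planned adjustment cannot work.** It is impaired for one class of covariate. Adjustment for MS drugs, comorbidities and other factors is untouched.
- **That unrecorded use will be coded as no use.** Nothing in the protocol says so, and the CRF is not shown.
- **That only birth-defect cases are asked about medicines later.** Table 2 asks all prospective women at three further interviews.
- **That covariate data will differ between cases and non-cases.** No section says that the Targeted Follow-up Form feeds the analysis covariates, and Table 2 does not mark concomitant medications in that column. The form is triggered by a birth defect, so it creates no general asymmetry for spontaneous abortion, the primary outcome. What remains is a caution: those data should not be used as a covariate unless every woman is asked in the same way.

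None of this removes the mismatch between an enrolment-based window and a periconceptional variable.

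**Conclusion.** The point holds for non-MS co-medication, folic acid and herbal products, and should be fixed. Under the assumptions above, a woman who enrols at week 12, within the protocol's own target, has about 47% of weeks 5–10 covered and conception not covered; from week 16 none of weeks 5–10 is covered. The exposed group therefore cannot reliably supply the periconceptional folic acid and other-medication variables listed in 9.7.4.3. Any adjustment for other medications under 9.7.5 would be impaired and not comparable between groups.

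How many women this touches cannot be computed, because the protocol gives no distribution of gestational age at enrolment. Sample size, outcome ascertainment and the calculation of the unadjusted relative risk do not change. For retrospective pregnancies the loss can be complete. It matters there for description and signal detection (9.7.4.2 and 9.9 look to these cases for a malformation pattern and for signals), not for a comparison.

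**What to change.** Reword 9.6.2.1 and Table 2, footnote f, identically. For every prospective and retrospective woman, record all medicines, supplements (folic acid included) and herbal products, with start and stop dates, from one month before LMP to the end of pregnancy. Keep MS medications from onset. The protocol does not define periconceptional in 9.7.4.3, so confirm the window used in the comparison registry (OBS13499) and align with it. State that medication data from the Targeted Follow-up Form will not serve as a covariate unless collected in the same way for all women.

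The LMP date is already collected and the interviews are already held, so the cost is CRF and interview wording. No sample size or power figure changes. The downside is longer recall for women who enrol late. The change is best made early, because later recall may not restore what was not asked of women enrolled under the current wording.

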9.6.2.2 Data collected from Health Care provider (HCP) by National Coordinator

All data collected by HCP will be submitted to respective National Coordinator.

National Coordinator will review the medical records provided by HCPs and will contact HCPs, whenever needed, will complete collection of data with queries and clarifications, in order to confirm pregnancy outcomes - by telephone, faxed/mailed forms or email.

For live birth outcomes, infant HCPs will be contacted 1 year post-delivery to complete a standard questionnaire containing information on infant size, postnatal complications, congenital anomalies, method of infant feeding, and targeted infant medical history (e.g., neonatal Grave's disease, recurring or serious infections, autoimmune disorders).

Information to be verified by HCPs includes:

- Pregnancy outcome (live birth, spontaneous abortion, stillbirth, induced abortion) and type (singleton or multiple).
- For live births
 - Gender, gestational age at delivery, mode of delivery, type/length of hospital stay, maternal and neonatal complications, maternal weight gain, presence or absence of major and minor structural defects, Apgar scores, birth weight, birth length, and head circumference.
- For other outcomes
 - Gestational age at time of event, pathology results if available, and presence or absence of major and minor structural defects. For stillborn infants gender, birth size, and autopsy results.

9.6.3 Site/Investigators questionnaire

Not applicable.

9.6.4 Patient/Subject tracking log (if applicable)

Not applicable.

9.6.5 Procedure for withdrawal of patients from study follow-up schedule

The HCPs and National Coordinators will endeavor to conduct follow-up in accordance with the protocol's study data collection schedule for all women enrolled in the study who are eligible, have provided informed consent, and have completed the initial enrolment interview. National Coordinator will make multiple attempts to contact patients via HCPs with valid contact information using multiple mechanisms (e.g., phone, fax, mail) before a woman is considered lost to follow-up. Women with missing pregnancy outcome information due to lost to follow-up will be described in study enrollment-related analyses but will be excluded from the denominator of outcome-related analyses.

Participation in the study is voluntary and women may withdraw consent to participate in follow-up visits at any time. For women who withdraw consent, study participation for both the woman and her infant will terminate immediately upon her request. Once a woman is withdrawn from the study, routine pharmacovigilance follow-up procedures will be applied for all ongoing adverse events.

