9.2.3 Analysis population(s)

The primary analysis population will include all women (prospectively) enrolled in the study who meet the study inclusion criteria and have pregnancy outcome data recorded. Outcomes for the primary analysis population will primarily be compared with pregnancy outcomes in unexposed external comparison groups.

Ascertainment of pregnancy outcomes will be considered completed when:

- Pregnancy outcome is known and was not a live birth, or
- Pregnancy outcome was a live birth and the 1-year post-delivery follow-up has been completed, or
- The woman has been classified as lost to follow-up, or
- The woman has withdrawn informed consent prior to ascertainment of pregnancy outcome.

Otherwise; the pregnancy outcome will be considered as pending.

For the analysis, descriptive analyses of baseline characteristics of the additional populations of all enrolled women (including women whose pregnancy outcome data are unknown, such as lost to follow up), and the subset of women whose pregnancy outcome data are unknown, will also be calculated.

Retrospective pregnancy population will provide qualitative data which will be descriptively analyzed independent of the prospectively collected primary analysis population.

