9.7 DATA ANALYSIS

9.7.1 Primary analysis

The primary analysis population will include all women enrolled in the study prospectively who meet the study inclusion criteria and have pregnancy outcome data recorded. Outcomes for the primary analysis population will primarily be compared with pregnancy outcomes in unexposed external comparison groups. Ascertainment of pregnancy outcomes will be considered completed when:

- Pregnancy outcome is known and was not a live birth, or
- Pregnancy outcome was a live birth and the 1-year post-delivery follow-up has been completed, or
- The woman has been classified as lost to follow-up, or
- The woman has withdrawn informed consent prior to ascertainment of pregnancy outcome.

Otherwise, the pregnancy outcome will be considered as pending.

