11.1 SAFETY INSTRUCTIONS

11.1.1 Definitions of Adverse Event (AE) and Serious Adverse Event (SAE)

An **Adverse Event (AE)** is any untoward medical occurrence or clinical investigation in a patient administered a pharmaceutical product and which does not necessarily have to have a causal relationship with this treatment.

A **Serious Adverse Event** is an adverse event that at any dose:

- Results in death or;
- Is life-threatening or;
- Requires inpatient hospitalization or prolongation of existing hospitalization or;
- Results in persistent or significant disability/incapacity or;
- Is a congenital anomaly/birth defect;
- Is a medically important event;
- Suspected transmission of infectious agent; is any suspected transmission of an infectious agent via a medicinal product (e.g., product contamination).

Note: The term "life-threatening" in the definition of "serious" refers to an event in which the patient was at risk of death at the time of the event; it does not refer to an event which hypothetically might have caused death if it were more severe.

For this study, SAEs also include specific pregnancy outcome related events: all spontaneous abortions, stillbirths, neonatal deaths, and foetal major malformations occurring in a LEMTRADA-exposed pregnancy.

Medical and scientific judgment should be exercised in deciding whether expedited reporting is appropriate in other situations, such as important medical events that may not be immediately life threatening or result in death or hospitalization but may jeopardize the patient or may require intervention to prevent one of the other outcomes listed in the definition above. Examples of such events may include, but are not limited to malignancies, events requiring intensive treatment in an emergency room or at home, as allergic bronchospasm or convulsions, that do not result in inpatient hospitalization.

The following events should be reported in the same fashion as SAEs (within 24 hours within becoming aware of the event) if seriousness criteria, including "medically important" are met: autoimmune mediated conditions, including immune thrombocytopenia; thyroid disorders; other non-thyroid autoimmune diseases as nephropathies (including anti-glomerular basement membrane (anti-GBM) disease), cytopenias; serious infections (including serious opportunistic infections); pneumonitis, malignancy and symptomatic overdose (serious or non-serious) with LEMTRADA.

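### Section 9.6.5 turns withdrawal from follow-up visits into the end of all participation for mother and infant, so outcomes that provider records could supply are lost without need

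*Protocol*

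**What the plan says.** Section 9.6.5 describes the right to withdraw in terms of visits: "Participation in the study is voluntary and women may withdraw consent to participate in follow-up visits at any time". The next sentence sets the consequence: "For women who withdraw consent, study participation for both the woman and her infant will terminate immediately upon her request". The only activity it names afterwards is safety follow-up: "Once a woman is withdrawn from the study, routine pharmacovigilance follow-up procedures will be applied for all ongoing adverse events".

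Other sections follow the same line. Sections 9.2.3 and 9.7.1 count ascertainment as complete when "The woman has withdrawn informed consent prior to ascertainment of pregnancy outcome". Table 2, footnote g, restricts the 1-year infant questionnaire: "For live-birth outcomes only, if woman has not withdrawn consent". The primary population consists of prospectively enrolled women "who meet the study inclusion criteria and have pregnancy outcome data recorded".

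The protocol also provides a route to outcomes that does not run through interviews. Under section 9.6.2.1, where local legislation allows, "signature of ICF will mean that the pregnant patient consents that medical records of herself and of the infant can be released by the HCP"; the recipient is the National Coordinator. Under section 9.6.2.2 the National Coordinator confirms pregnancy outcomes from provider records, and the infant's provider completes the 1-year questionnaire.

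**The concern.** A woman can mean two different things by withdrawing: that she wants no more interviews, or that she no longer agrees to any use of her and her child's records. Section 9.6.5 applies the second consequence to both. For a woman of the first kind, the registry gives up a pregnancy outcome and an infant-year status that her providers could still report under the consent she signed.

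This sits badly with section 9.9. That section relies on retaining enrolled women to limit selection bias, and it asks for loss to be kept to a minimum because exposed pregnancies are rare and hard to enrol. Withdrawal may also be related to the outcome, for instance after a loss or an abnormal finding. Outcomes missing for that reason can move the exposed rate in either direction.

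A second, smaller gap concerns what may count after withdrawal. Pharmacovigilance continues for ongoing adverse events, and the protocol does not say whether an outcome learned that way enters the registry rates.

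**Working it through.** **Inputs** (protocol section 9.5.1 and Table 1): 204 women enrolled, 193 with outcome, about 5% missing outcomes; background spontaneous abortion rate 13.5%; detectable relative risk 2.0 (27.0%). Section 9.5.2 gives 117 comparators. No withdrawal count is given, so the whole missing-outcome allowance is used as an assumption.

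**1. The plan's own figures.** 204 × 0.95 = 193.8, stated as 193, which leaves 204 − 193 = 11 women. Power for 27.0% against 13.5% with 193 and 117 women, one-sided 0.025, is 78.1% by exact enumeration of Fisher's test and 81.3% by the pooled z approximation. The stated 80% is reproduced. With all 204 exposed women it would be 79.5% (Fisher), so recovering the outcomes barely changes power. The issue is possible bias and lost data.

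**2. Outer bounds when the 11 outcomes are missing.** Expected events among 193: 193 × 0.135 = 26.1, taken as 26.
- None of the 11 had a spontaneous abortion: 26/204 = 12.7%, a ratio of 0.94 to 13.5%.
- All 11 did: (26 + 11)/204 = 37/204 = 18.1%, a ratio of 1.34.

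At 27.0%, 193 × 0.27 = 52.1, taken as 52. The bounds are 52/204 = 25.5% and 63/204 = 30.9%, around 52/193 = 26.9%. If withdrawal is unrelated to outcome, the expected rate does not change.

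**3. Selective inclusion through the safety channel.** Suppose that all 11 are withdrawals with the same risk as the rest, that every spontaneous abortion among them is added, and that no other outcome is. The rate is then (193p + 11p)/(193 + 11p).
- p = 0.135: (26.055 + 1.485)/(193 + 1.485) = 27.54/194.485 = 14.2%, a ratio of 1.05.
- p = 0.27: (52.11 + 2.97)/(193 + 2.97) = 55.08/195.97 = 28.1%, a ratio of 1.04.

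**4. The passages side by side.**

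| Question | Protocol |
|---|---|
| What may be withdrawn? | Follow-up visits (9.6.5) |
| What ends? | All participation, mother and infant (9.6.5); infant questionnaire (Table 2, footnote g) |
| Does the outcome need a further interview? | Not where provider records may be released (9.6.2.1, 9.6.2.2) |
| Do safety reports received after withdrawal count in the rates? | Not stated |

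**The case against.** Ending collection when consent is withdrawn is proper, and nothing here disputes that for a woman who withdraws fully. A missed interview is not a withdrawal, and termination follows only when the woman asks for it. The consent form is not part of the text reviewed and may already separate visits from record release. Release under the signed form applies only where local law permits. Elsewhere, section 9.6.2.1 has separate release forms sent after the outcome interview, so a two-level rule gains less there. The protocol does describe women with unknown outcomes separately (9.2.3, 9.7.2) and discusses bias from loss to follow-up (9.9). All of this stands, and it limits the point to a clarification. It does not remove the gap, because section 9.6.5 as written still has one consequence for both kinds of withdrawal.

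A reader might go further and infer that outcomes are lost for uneventful pregnancies but kept for troubled ones. The documents do not support that:
- No section feeds pharmacovigilance information into the registry outcomes. As written, outcomes after withdrawal are lost whether or not the pregnancy was eventful.
- The safety route covers events ongoing at withdrawal. A spontaneous abortion known before withdrawal is already an outcome and, under section 11.1.1, a serious adverse event ("all spontaneous abortions, stillbirths, neonatal deaths, and foetal major malformations occurring in a LEMTRADA-exposed pregnancy"). One that first occurs afterwards is not covered. What remains is a complication that is ongoing at withdrawal and later ends in loss.
- Section 9.2.4.2 sends women who decline participation to separate pregnancy reports whether or not they have an adverse event, and it is silent on withdrawn women. That safety follow-up is the only source after withdrawal is therefore not established.

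Nor can one infer a difference from the comparison cohorts. The protocol does not describe the withdrawal or safety procedures of the registry they come from.

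**Conclusion.** The point holds as an avoidable loss of outcome data. Section 9.6.5 merges stopping visits with ending all participation, although the protocol has a provider-record route that needs no further interview where consent and local law allow. For a woman who withdraws after delivery, the pregnancy outcome is already known and the loss is the infant year.

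The size is uncertain. If all 11 missing outcomes were withdrawals, the bounds around a 13.5% rate are 12.7% to 18.1%. They describe any 5% of missing outcomes at their extremes and are not an estimate of bias. Selective counting of losses from safety reports is a risk that arises from silence and is not a stated rule. It is worth at most about a 5% relative increase under the assumptions in step 3 of the working. The stated power does not depend on this point. It is a cheap improvement and no threat to the study's validity. It belongs in the protocol and consent form, because a later analysis plan cannot recover data that were never collected.

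**What to change.** Replace the single rule in section 9.6.5 with two levels:

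- **Withdrawal from interviews only.** The woman is not contacted again. Pregnancy outcome and 1-year infant status are still obtained from the providers where her consent and local law allow, and she stays in the primary population.
- **Full withdrawal, including record release.** All registry collection stops, and data up to that date are kept.

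Add one sentence: outcomes learned only through pharmacovigilance after full withdrawal are listed but enter neither the numerator nor the denominator of the rates. Bring Table 2 footnote g and sections 9.2.3 and 9.7.1 into line, and also the consent form if it does not already make the distinction.

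The cost is protocol and consent wording, one case report form field for the level of withdrawal, and an ethics resubmission. No visits or staff are added. The gain is smaller in countries that require a separate record release.
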